This study will be conducted for research purposes only and is not intended to be used to support safety and efficacy in a regulatory submission.

14 INTRODUCTION

Scleral contact lenses are rigid gas permeable lenses designed to rest on the sclera while vaulting over the cornea with a fluid reservoir. (1) The use of scleral contact lenses has become the current standard of practice as a nonsurgical management of corneal ectasia and ocular surface diseases.(1–3) Currently, the long term impact which scleral contact lens wear has on the physiology of the cornea and limbus is not known. Tear film analysis of changes in levels of proteinases and cytokines have helped researchers gain a better understanding of pathophysiology in complications in soft contact lenses wearers (4,5), dry eye (6), and keratoconus (7,8). Understanding factors that influence tear film composition may aid in better understanding of the impact of scleral contact lenses on the health of the cornea, specifically, the mechanism of complications commonly associated with the usage of these large gas permeable lenses.

14 PURPOSE AND HYPOTHESIS

The purpose of this study is to investigate changes in the level of inflammatory mediators in the tear film of scleral contact lenses wearers. The hypothesis is that scleral contact lens wear is associated with inflammation in the tear film. Furthermore, the level of proteases and cytokines will be altered in samples collected post scleral lens wear compared to those collected pre-lens wear. Additionally, the amount of alteration will correlate to the fitting characteristics in the limbal zone of the scleral lenses.

14 OBJECTIVES

We propose to take a sample of keratoconic participants and fit them in scleral lenses and:

1. To collect and examine tear samples before and after 6-8 hours of scleral lens wear.
2. To measure the level proteases and cytokines in each of the samples using enzyme-linked immunosorbent assays (ELISA)
3. To compare the results of varying limbal clearance in scleral lens fit.

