14 MATERIALS AND METHODS

13.1 STUDY DESIGN

12.1.1 OVERALL DESIGN

This will be a prospective cross-over, dispensing study design. The study will involve up to 20 keratoconic participants.

Participants will attend 1 screening/fitting visit wearing their habitual contact lenses where the two test lens designs will be fitted. There then will be a dispensing visit for each design (randomly selected) and a single follow up visit 2 weeks later after 6-8 hours of scleral lens wear. A washout period of a minimum of 72 hours will be applied between the cross-over of each lens design.

Lenses to be worn in this study will be made of Boston XO material and are approved by Health Canada. The lenses will have a diameter of 14.8 to 17.8mm with a high and low sagittal depth at the limbal zone. As to which of the two lenses is being assessed, both the investigator and the participant will be masked.

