12.4.2 STUDY VISITS

This study will involve 6 visits over 5 study days. The total time commitment for all study visits is approximately 6 hours. The total study visit time commitment may be different for each participant, as the needed visit time will depend on how easily the lenses can be fitted.

The first visit will involve screening of the participants and baseline measurements. The investigator will determine the eligibility of the participant using the inclusion/ exclusion criteria. Ineligible participants will be discontinued from the study. The investigator will also perform baseline tear collection.

At the lens fitting appointment, the participants will be fitted with the scleral contact lenses based on the baseline measurement obtained at the screening appointment. Participants will be instructed on insertion, removal, and proper handling of the lenses.

At each of the lens delivery appointments, the researcher will deliver the study lenses. Measurements, including bulbar hyperemia and pre-lens NITBUT, will be obtained while the participants are wearing the lenses.

After the participant has worn the lenses during the day for two weeks, the participant will return for a follow up visit. At each of the follow up appointments, the lens fit and measurements, including bulbar hyperemia and pre-lens NITBUT, will be repeated while the participants are wearing the lenses. Tear samples will be collected from the study lenses after lens removal.

A wash-out period of minimum of 72 hours is required between the first follow up visit and the second lens delivery visit.

Table 1 provides a summary of the study visits.

Table 1: Summary of visits

Visit code	Visits	Time
0-0	Screening and baseline measurements	1hr±½ hr
1-1	Lens fitting	1hr±½ hr
2-1	Lens Delivery visit - Lens 1	1hr±½ hr
2-2	Follow-up visit - Lens 1	1hr±½ hr
3-1	Lens Delivery visit - Lens 2	1hr±½ hr
3-2	Follow-up visit - Lens 2	1hr±½ hr

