13.5 STUDY PROCEDURES

12.5.1 SCREENING, BASELINE AND EXPERIMENTAL MEASUREMENTS

Screening & Baseline procedure: Participants will present to the screening visit. Their corneal sagittal depth which will be measured with the Visante OCT, auto-refraction and associated visual acuity measurements and corneal topography carried out and biomicroscopy performed, along with hyperemia imaging and pre-lens non-invasive tear break up time. Eligibility will be confirmed and a baseline biomicroscopy assessment will be performed. (Visit 0-0)

Bulbar and Limbal Redness assessment: The eyes of the participants will be imaged using the Keratograph® 4. Participants will be asked to be seated at the Keratograph 4 instrument and will be asked to blink 2-3 times and hold their eye open for a few seconds until the instrument software takes a picture of the eye. This image will be repeated three times.

Flush tear collection method: This procedure entails the instillation of a small amount non-preserved saline, 60 μ L, into the inferior palpebral fold. After which, the fluid can be collected with a micro-capillary tube. (9,10) All samples are collected by the researcher. (Visit 0-0)

Fitting of the semi-scleral lenses: Participants will be fitted each of the two sets of semi-scleral lenses of varying sagittal depth at the limbal zones. Fittings will be done using the corneal sagittal depth which was measured at the screening/baseline visit with the Visante OCT. The lenses will be made of the same gas permeable lens material Boston XO. The lens fit will be evaluated; over-refraction and visual acuity determined. Participants will be instructed on insertion, removal, and proper handling of lenses. (Visits 1-1)

Video Imaging procedure with test lenses: The lens fitting will be imaged using a video-slit lamp and the Visante OCT after the lens delivery appointment (Visits 2-1 & 3-1) and at the follow up appointment. (Visits 2-2 & 3-2)

Pre-lens Non-invasive tear break up time (NITBUT) with test lenses: Pre-lens NIBUT will be measured with the study lens after lens delivery (Visits 2-1 & 3-1) as well as at the follow up visits (Visits 2-2 & 3-2). Participants will be asked to be seated at the Keratograph 4 instrument and will be asked to blink 2-3 times and hold their eye open for a few seconds until the instrument software takes a measurement of the NITBUT. This measurement will be repeated three times.

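### Objective 1 claims a tear-film change over 6-8 hours of scleral wear, but the only pre-wear sample is a screening flush taken at least 14 and 31 days before the two post-wear samples

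*Combined protocol and SAP*

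**What the plan says.** Objective 1 (Objectives section) is "To collect and examine tear samples before and after 6-8 hours of scleral lens wear". The Purpose and Hypothesis section predicts that "the level of proteases and cytokines will be altered in samples collected post scleral lens wear compared to those collected pre-lens wear".

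On the pre-wear sample, section 12.1.1 states: "Participants will attend 1 screening/fitting visit wearing their habitual contact lenses where the two test lens designs will be fitted". Section 12.4.2 (Study Visits) says of the first visit: "The investigator will also perform baseline tear collection". Section 12.5.1 describes a flush method using 60 microlitres of saline and assigns it to visit 0-0 only. Table 2 lists a baseline collection once, under visit 0-0.

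On the post-wear sample, section 12.4.2 says: "After the participant has worn the lenses during the day for two weeks, the participant will return for a follow up visit". Section 12.1.1 adds that this visit follows 6-8 hours of wear. Section 12.4.2 and Table 2 both take the follow-up sample from the study lens once it has been removed.

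On lens-free time, the only stated interval is in sections 12.1.1 and 12.4.2: "A wash-out period of minimum of 72 hours is required between the first follow up visit and the second lens delivery visit". Table 3 (section 13.1, Statistical Analysis) lists one contrast, lens 1 against lens 2.

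**The concern.** A change over 6-8 hours needs a sample shortly before the lens goes in and another 6-8 hours later. No tear collection is listed at fitting, at either delivery visit, at the end of the washout, or before insertion on a follow-up day. The only value that can serve as the pre-wear level comes from a different day, under uncontrolled lens status, and by a different collection method.

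The inference from Objective 1 and the pre/post hypothesis is at stake. A rise could be reported as an inflammatory response to a day of scleral wear when it reflects two weeks of wear or the switch from flush fluid to lens fluid. A null result could mean no response, a baseline already raised by the habitual lens, or a difference in dilution that hides a response. No analysis can separate these afterwards, because the samples needed will not exist.

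**Working it through.** There is no stated figure to reproduce. Section 12.2.1 gives a sample of 15-20 without a significance level, power, effect size or SD. The check is therefore a count, an elapsed-time calculation and a look at what each difference can estimate. Visit codes are those of Table 1; Table 2 numbers the delivery and follow-up visits differently.

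**Tear collections per participant** (12.4.2, 12.5.1, Table 2)

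| Visit | Tear collection | Method |
|---|---|---|
| 0-0 screening and baseline | 1 | saline flush from the eye |
| 1-1 fitting | none | – |
| 2-1 delivery, lens 1 | none | – |
| 2-2 follow-up, lens 1 | 1 | fluid from the removed lens |
| 3-1 delivery, lens 2 | none | – |
| 3-2 follow-up, lens 2 | 1 | fluid from the removed lens |

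The total is 3 collection occasions per participant: 3 × 15 = 45 to 3 × 20 = 60. One is pre-wear and two are post-wear, and no pre-wear sample falls on the day of a post-wear sample.

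**Minimum age of the baseline**, taking no delay between 0-0 and 2-1 and counting 72 hours as 3 days:

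- At visit 2-2: 14 days.
- At visit 3-2: 14 + 3 + 14 = 31 days.

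Any gap between screening and delivery adds to both figures.

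**What the pre/post difference contains.** For lens k:

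post_k − base = (effect of 6-8 hours that day) + (effect of two weeks of daily wear) − (residual habitual-lens effect at 0-0) + (calendar time) + (lens fluid versus flush), plus any carryover when k = 2.

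Each lens gives one such difference, and both use the same baseline. The first term cannot be recovered from them.

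**What the lens comparison contains.**

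(post_1 − base) − (post_2 − base) = post_1 − post_2.

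The baseline drops out, along with its age, lens status and collection method. Both remaining samples come from removed lenses under the same schedule. A numerical check with simulated values for 20 participants gave the same identity.

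**The case against.** The strongest reply is that visit 0-0 does precede all study-lens wear, and that 6-8 hours can be read as a standardised wear time on the follow-up day. On that reading a baseline-to-follow-up change can be computed and the fault is loose wording. The first part stands: a change is computable. It is not the change Objective 1 names, and the wording decides what the trial may conclude.

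It is also fair that the only tabulated contrast, and Objective 3's direct comparison of the two lenses, do not depend on the baseline. That stands in full. The registration section describes the work as early feasibility, which bears on how much new sampling to ask for but not on whether an objective should match its data.

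A reader might infer more than the documents support in two places:

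- **That the difference is simply scleral minus habitual wear, with lens 1 following habitual wear directly.** Section 12.1.1 speaks of arrival at a combined screening/fitting visit, whereas 12.4.2 separates the two. No text says when habitual lenses come off before the baseline sample, or whether they are worn up to visit 2-1. The lens-free time is unstated, not known to be zero.
- **That the baseline was taken in existing scleral wearers.** The exclusion criteria do not rule them out. The risks and benefits section, however, expects participants to meet a new modality, and the fitting visit teaches insertion and removal. This points towards new wearers without settling the matter.

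**Conclusion.** As written, Objective 1 and the pre/post hypothesis claim a 6-8 hour change that the schedule cannot isolate. What the data can show is a change from one screening sample, with uncontrolled lens-free time, to a lens-fluid sample at least 14 days later for lens 1 and at least 31 days later for lens 2. The conclusion rests only on the listed visits and the stated two-week and 72-hour intervals. It does not extend to the lens 1 versus lens 2 comparison.

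A reader might also infer a definite loss of power from a raised baseline. For a paired t-test at two-sided 5%, 80% power needs an effect of about 0.66 SD at n = 20 or 0.78 SD at n = 15. If one third of that effect were already in the baseline, power would be about 46%; if one half, about 29%. These fractions are assumptions and the power values follow from them. The documents give no SD, effect size or habitual-lens effect, and Table 3 lists no pre/post test, so the figures are illustrative only and the point does not rest on them.

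**What to change.** **Needed, at the cost of wording.** Restate Objective 1 and the hypothesis as change from a screening baseline (habitual lens wearers, lens-free time not controlled) to after two weeks of daily scleral wear, sampled at 6-8 hours. State that this change will not be attributed to 6-8 hours of wear, or to scleral wear alone, and that the two collection methods differ.

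**Needed, at the cost of two form entries at visit 0-0.** Record same-day habitual wear time and time since lens removal before the sample. Table 2 already collects contact lens details at that visit, so lens type needs no new item if it is captured there.

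**Needed, to reconcile the text.** The 72-hour interval is stated only before lens 2. Sections 12.1.1, 12.4.2 and 12.5.1 must be reconciled on lens-free time before the baseline sample and before lens 1, and on whether screening and fitting are one visit or two.

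**Optional.** Take a pre-insertion sample at existing visits 2-1 and 3-1 as period baselines. This adds two collections and their ELISA wells per participant, from 3 to 5, or from 45-60 to 75-100 occasions in all. It gives each period its own baseline, but that baseline would still precede follow-up by two weeks, so 6-8 hours would not be isolated. At 2-1 no lens-free interval is currently stated. The addition helps only if the collection method matches the post-wear sample, or if the mismatch is declared as a limitation.

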14 MATERIALS AND METHODS

13.1 STUDY DESIGN

12.1.1 OVERALL DESIGN

This will be a prospective cross-over, dispensing study design. The study will involve up to 20 keratoconic participants.

Participants will attend 1 screening/fitting visit wearing their habitual contact lenses where the two test lens designs will be fitted. There then will be a dispensing visit for each design (randomly selected) and a single follow up visit 2 weeks later after 6-8 hours of scleral lens wear. A washout period of a minimum of 72 hours will be applied between the cross-over of each lens design.

Lenses to be worn in this study will be made of Boston XO material and are approved by Health Canada. The lenses will have a diameter of 14.8 to 17.8mm with a high and low sagittal depth at the limbal zone. As to which of the two lenses is being assessed, both the investigator and the participant will be masked.

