12.3.5 TEAR FILM ANALYSIS

Tear film analysis is performed using antigen capture enzyme linked immunosorbent assay (ELISA). (5) After collection, the tear samples are stored at -80°C until analysis. Preparation of the samples includes dilution with phosphate buffered saline (PBS) containing 1% (w/v) bovine serum albumin and incubation with specific antigen. The tears are assayed for specific proteinase and cytokines using commercially available ELISA kits. Preparation and analysis of samples are as per instructions supplied by manufacturers.

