14 STATISTICAL ANALYSIS AND DATA MANAGEMENT

13.1 STATISTICAL ANALYSIS

All data described above will be analysed at the University of Waterloo from the eye(s) wearing the semi-scleral contact lens(es). Data analysis will be conducted using Statistica 12. Descriptive statistics will be provided on information regarding baseline variables (age, gender, sagittal depth distribution, etc.). Table 3 lists the primary outcome variables and anticipated statistical procedures.

Table 3: Statistical procedures

Variable	Analysis	Statistical test
Parametric (tear clearance, NIBUT, comfort ratings, tear components)	Comparison of lens 1 to lens 2	ANOVA Paired t-test

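### The two lenses may hold different volumes of the fluid that is sampled, and the protocol text specifies no volume correction, so a lens difference in tear components cannot be separated from dilution

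*Combined protocol and SAP*

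**What the plan says.** The Introduction describes scleral lenses as designed to "rest on the sclera while vaulting over the cornea with a fluid reservoir". Section 12.1.1 sets the randomised contrast: "The lenses will have a diameter of 14.8 to 17.8mm with a high and low sagittal depth at the limbal zone". Section 12.4.2 gives the source of the post-wear sample: "Tear samples will be collected from the study lenses after lens removal". Table 2 repeats this for the follow-up visits.

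Section 12.3.5 describes the assay: "Preparation of the samples includes dilution with phosphate buffered saline (PBS) containing 1% (w/v) bovine serum albumin and incubation with specific antigen". It mentions no sample volume, total protein or dilution marker. In Table 3 (section 13.1) one row covers the outcomes, "Parametric (tear clearance, NIBUT, comfort ratings, tear components", with a lens 1 to lens 2 comparison by ANOVA and paired t-test and no volume term.

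The third objective is to compare results across limbal clearances. The Purpose and Hypothesis section adds that "the amount of alteration will correlate to the fitting characteristics in the limbal zone of the scleral lenses".

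**The concern.** The randomised factor may change the volume of the compartment that is sampled. A deeper limbal zone leaves more space under the lens. If the eye releases the same amount of a mediator under both lenses and the fluid stays in place, the deeper lens yields a lower concentration for geometric reasons alone.

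Randomisation, masking and the crossover do not remove this, because the effect belongs to the lens and not to the participant, the period or the assessor. It also lies along limbal clearance, the axis of the hypothesis. It could therefore produce an apparent lens effect and a negative correlation with clearance, or hide a real increase under the deeper lens.

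This is separate from the contrast between the baseline flush sample, collected after 60 µL of saline is instilled (section 12.5.1), and the post-wear sample from the lens. Repairing that contrast would leave the lens-versus-lens comparison as it is.

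**Working it through.** **Inputs from the document.** Up to 20 participants (15-20 in section 12.2.1), crossover, sampling after 6-8 hours of wear, paired comparison of lens 1 with lens 2. The document gives no clearance, reservoir volume, fill fluid, assay variability, significance level or power, so it has no figure of its own to reproduce here. Everything below rests on assumptions, with a two-sided 5% level.

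**Step 1: volume (assumed geometry).** Vaulted zone of radius 6.5 mm; limbal annulus from 5.0 to 6.5 mm; mean vault 0.15-0.30 mm; extra limbal clearance 0.05-0.10 mm; the two lenses otherwise alike.
- Annulus area: π × (6.5² − 5.0²) = 54.2 mm². Added volume: 54.2 × 0.05 to 0.10 = 2.7 to 5.4 µL.
- Base volume: π × 6.5² × 0.15 to 0.30 = 19.9 to 39.8 µL.
- Volume ratio: from 1 + 2.7/39.8 = 1.07 to 1 + 5.4/19.9 = 1.27.
- Concentration ratio with no exchange: 1/1.07 = 0.94 to 1/1.27 = 0.79, that is 6% to 21% lower.

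A second assumed geometry (annulus 5-7 mm, vault 0.2-0.4 mm, extra clearance 0.05-0.15 mm) gives volume ratios of 1.06-1.37 and readings 6-27% lower.

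**Step 2: false positives with no exchange.** A 50% CV for the paired difference corresponds to a log SD of √ln(1 + 0.5²) = 0.472. The standardised shift is ln(volume ratio)/0.472, and the rejection probability comes from the noncentral t distribution.

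| Volume ratio | Shift (SD) | n = 15 | n = 20 |
|---|---|---|---|
| 1.1 | 0.095/0.472 = 0.20 | 11% | 14% |
| 1.2 | 0.182/0.472 = 0.39 | 29% | 37% |

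The rates depend heavily on the SD. At ratio 1.2 and n = 20 they are 73%, 34% and 16% for log SDs of 0.3, 0.5 and 0.8.

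**Step 3: tear exchange.** With constant release and exchange flow Q, concentration after time t is proportional to (1 − exp(−Qt/V))/Q. Once the reservoir equilibrates, V drops out. For a volume ratio of 1.2, a base of 20-60 µL and t of 6-8 hours:

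| Q (µL/min) | High/low concentration ratio |
|---|---|
| 0 | 0.83 |
| 0.1 | 0.87-0.95 |
| 0.5 | 0.97-1.00 |

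Step 2 is therefore the unfavourable end of the range.

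**Step 4: which decision rule helps.** Simulated trials with n = 20, log SD 0.472, no exchange, no true effect on amount and volume known without error:

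| Rule for claiming a lens effect | Ratio 1.1 | Ratio 1.2 |
|---|---|---|
| Concentration significant | 13.8% | 37.3% |
| Concentration significant, amount merely in the same direction | 13.8% | 36.2% |
| Both significant, same direction | under 3% | under 3% |

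Agreement in direction alone does almost nothing: a concentration difference large enough to be significant usually keeps its sign after ln(volume ratio) is added back. Requiring both to be significant works because amount is unbiased in this scenario. At full equilibration the roles swap (concentration fair, amount biased upward under the deeper lens), and the same rule protects by the same argument.

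**The case against.** The strongest reply is that the size is unknown and may be negligible. Step 3 shows that moderate exchange over 6-8 hours removes most of the effect. The document does not say that a participant's two lenses share diameter and central vault. This stands: the 6-21% range and the 14% and 37% rates are conditional, not estimates for this trial.

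A second reply concerns the target. The hypothesis speaks of the level of mediators. If a deeper reservoir lowers the concentration facing the limbus, that is a real consequence of the fit. It misleads only when read as a difference in release. This also stands, and it is why the fix limits the interpretation and keeps the concentration analysis.

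Third, amount is not a cleaner measure in every case. It is biased the other way if the reservoir equilibrates with tears, and recovered volume falls short of reservoir volume if fluid is lost at removal. This is a reason to report both measures, not to replace one with the other.

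Finally, a reader might infer that the trial will not record volume at all, or that its unit is certainly concentration. The document does not support either. Table 2 sends tear collection to the Biomicroscopy Form (Appendix 4), whose content is not in the text reviewed, and no unit is stated for tear components. What can be said is that the protocol text specifies neither a volume nor a correction.

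**Conclusion.** The point holds as a conditional one. Followed as written, the plan cannot distinguish a lens effect on mediator release from dilution in a reservoir whose volume depends partly on the randomised lens. The bias, if present, lowers readings under the deeper lens: about 6-21% under the first assumed geometry with no exchange, and close to zero with brisk exchange. With no exchange, a 50% CV and 20 participants, a 10% or 20% volume difference raises the false-positive rate from 5% to about 14% or 37%. The geometry, CV, exchange rate and likeness of the two lenses are all assumptions.

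A reader might go further and infer that any lens difference or clearance correlation from this trial would be an artefact. The document does not support that: it gives no clearance, volume or exchange rate from which the bias could be shown to be material. The change is worth making because it is cheap and because the recovered volume cannot be reconstructed once samples have been diluted and assayed.

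**What to change.** 1. In section 12.5.1, add a step to record the volume recovered from each lens at visits 2-2 and 3-2, with a field on the collection form if there is none.
2. Estimate reservoir volume for each lens from the OCT images that section 12.5.1 already plans at visits 2-1, 2-2, 3-1 and 3-2.
3. In section 13.1, state the unit for tear components. Pre-specify a sensitivity analysis that reports amount (concentration × volume) beside concentration, for both the lens comparison and the clearance correlation.
4. State the interpretation rule in advance: a lens difference is attributed to mediator release only if concentration and amount both show it, in the same direction, at the chosen significance level. Otherwise it is reported as not separable from dilution.
5. Optionally, normalise to total protein where sample volume allows.

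The cost is one volume reading per sample, measurement of images already taken and a second set of estimates. The downsides are noise in the volume estimate, fluid lost at lens removal, the opposite bias in amount if the reservoir equilibrates with tears, and some loss of power from requiring both results. No visit is added and clinical management does not change.

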13.2 RETENTION OF STUDY RECORDS AND DATA

Records and data from this study will be retained for a minimum of 25 years. Paper copies of study data will be safely held in a secure storage cabinet in a locked office at the School of Optometry and Vision Science, University of Waterloo and will be only available to personnel involved in the data collection of this study. The electronic research data will be encrypted as per Guidelines laid out by UW Information and Systems Technology and be stored on a password protected server held in a locked office at the School of Optometry and Vision Science. The images we acquire, with all identifying information removed, will be kept on a secure password protected server stored in a locked office at the School of Optometry and Vision Science. Image data will be saved using a coded file name associated with each participant, and the list of the participants' names and corresponding numbers will be stored in a separate file at UW. Access to electronic data, images, photographs and videos is limited to authorized study personnel.

Records will be confidentially disposed of in accordance with the guidelines laid out by the University of Waterloo. More information regarding the University of Waterloo's policies on information security is available on the following website: <https://uwaterloo.ca/secretariat-general-counsel/policies-procedures-guidelines/policy-8>.

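### Investigator masking is stated but not supported by the described procedures, and it cannot hold for anyone who fits the lens or views its fit

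*Combined protocol and SAP*

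**What the plan says.** Section 12.1.1 describes a crossover of two lenses "with a high and low sagittal depth at the limbal zone", worn in random order, and adds: "As to which of the two lenses is being assessed, both the investigator and the participant will be masked". No other section says how masking is achieved.

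Section 12.5.1 says of the fitting visit: "Participants will be fitted each of the two sets of semi-scleral lenses of varying sagittal depth at the limbal zones". For the later visits it says: "The lens fitting will be imaged using a video-slit lamp and the Visante OCT after the lens delivery appointment", and it repeats that imaging at follow-up. In the numbering of Table 1 these are visits 2-1, 3-1, 2-2 and 3-2. Section 12.4.2 has the lens fit reassessed at follow-up, at the same visit as the redness, tear break-up and tear-sample procedures. Table 2 lists a slit-lamp lens examination at delivery and at follow-up. Table 3 lists tear clearance among the primary outcome variables, with break-up time, comfort ratings and tear components.

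Section 12.3.5 (tear film analysis) does not mention masking of the assay. The only coding described is in the record-retention section: "Image data will be saved using a coded file name associated with each participant".

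**The concern.** The feature that distinguishes the two lenses is the feature that the scheduled fit examinations are able to show. In a crossover the same eye is seen with both designs, so a relative difference in clearance may be enough to tell which lens is on. A person who fits, examines or images the lens cannot be expected to remain unaware of the design.

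A report that repeats the sentence in section 12.1.1 would claim a property that the described procedures do not deliver. Knowledge of the lens could affect outcomes that need judgement, chiefly clearance readings, slit-lamp findings and the discretionary decisions in the section on discontinuation. It could also reach the tear assay, the scientific focus of the study, if whoever runs it can see which lens a sample came from. The plan neither prevents that nor says that it happens.

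**Working it through.** The main check is textual.

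1. **Claim.** The investigator is masked to the lens being assessed (section 12.1.1).
2. **What differs.** High versus low sagittal depth at the limbus (section 12.1.1). This is the stated difference. The plan does not say that diameter is matched between a participant's two lenses, so it may not be the only one.
3. **When the difference is on view.** At fitting (visit 1-1), where both designs are tried and the fit evaluated, and at 2-1, 2-2, 3-1 and 3-2, through slit-lamp examination, video slit lamp and OCT (sections 12.4.2 and 12.5.1, Table 2).
4. **Whether it is also measured.** Tear clearance is in Table 3, and objective 3 concerns limbal clearance.
5. **Who does this.** Not stated. The fitting and imaging sentences are passive. An investigator, a researcher and a research assistant all appear, and none is given a masked or unmasked role.
6. **What separates knowledge of the lens from the outcomes.** Nothing is described: no lens code, key-holder, separate fitter, masked reader or masked assay analyst.

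Items 2 to 4 mean that masking cannot hold for whoever fits the lens or views its fit. Items 5 and 6 mean that the plan does not show this to be someone other than the investigator who assesses outcomes.

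**Size.** The plan gives no bias figure, so the following is sensitivity only. Inputs: n = 15 and 20 (section 12.2.1) and the paired t-test (Table 3). The two-sided 5% level and the bias b, in SDs of the paired difference, are assumptions. With no true lens effect, the t statistic is noncentral with n − 1 degrees of freedom and noncentrality b√n. The rejection probability is P(|T| > c), with c = 2.145 for n = 15 and 2.093 for n = 20.

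| Assumed b | b√n, n = 15 | Rejection, n = 15 | b√n, n = 20 | Rejection, n = 20 |
|---|---|---|---|---|
| 0.05 | 0.194 | 5.4% | 0.224 | 5.5% |
| 0.1 | 0.387 | 6.5% | 0.447 | 7.1% |
| 0.2 | 0.775 | 11.2% | 0.894 | 13.6% |
| 0.3 | 1.162 | 19.2% | 1.342 | 24.7% |

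The plan has no masking-related figure of its own to reproduce.

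**The case against.** The strongest reply is that the plan nowhere says that the investigator fits the lenses or takes the images. It has several staff, and a separate unmasked fitter is not excluded. That stands. A reader might infer that the investigator personally does both and that double masking does not exist. The documents support neither: the operators are unnamed, and participant masking is uncontradicted. What remains is that no separation of roles is described, and that even with a separate fitter, whoever views the fit at follow-up sees the distinguishing feature.

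Two further inferences also fail. The sentence "All samples are collected by the researcher" might be read as showing that staff aware of the lens collect the post-wear tears, but it belongs to the flush method at visit 0-0, before any study lens is worn. Post-wear samples come from the removed lens, and their collector is not named. The participant-linked file name is a confidentiality provision. It does not show that images or tubes lack a lens code, only that none is described.

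It can also be said that the main outcomes are instrument-based. This is largely fair. Section 12.5.1 has the Keratograph software take the redness picture and the break-up measurement, each three times, and it describes no operator selection of images. Section 12.3.5 refers to kit manufacturers' instructions and mentions no discretionary assay repeats. The risk is therefore lower for these outcomes than for clearance and slit-lamp findings. For the assay and any reading of redness images, however, that protection is secure only if the material is coded, which the plan does not say.

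Finally, this is a small early-feasibility study for a thesis, not meant for regulatory use. That limits the consequences but does not make the masking sentence accurate.

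**Conclusion.** The point holds in this form: investigator masking is stated, no described procedure supports it, and it cannot hold for staff who fit the lens or view its fit. Who those staff are is not given. Participant masking is asserted without a described method, but nothing contradicts it.

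The effect on error rates is unknown. The range runs from negligible (5.4% to 5.5% at 0.05 SD) to material (19.2% to 24.7% at 0.3 SD), and nothing in the documents favours one end. The upper figures should not be read as an estimate of actual bias. This should be corrected before the study starts. It does not prevent the study from proceeding, and no change in sample size follows.

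**What to change.** Replace the masking sentence in section 12.1.1 with a statement that participants are masked, that staff who fit, examine or image the lens are not, and that the ELISA and the reading of redness images are masked.

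To make that true, label tear tubes and Keratograph redness files with a random code that hides lens, period and visit. Have an existing team member who neither runs the assay nor reads the redness images hold the key, and open it only after those data are locked.

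Report tear clearance as an unmasked measurement. A coded file name cannot hide the design in an image of clearance.

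The cost is a coding list, the assignment of a key-holder within the present team, and a less favourable masking claim. Visits and clinical procedures are unchanged.
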